The efficacy and safety of palbociclib was assessed in PALOMA-1 trial: a randomized Phase 2 study of palbociclib in combination with letrozole versus letrozole alone. The study showed that participants who were treated with Ibrance® plus letrozole had median PFS of 20.2 months as compared to those treated with letrozole alone who reported median PFS of 10.2 months ($p=0.0004$).²⁴ Following its success, the Food and Drug Administration (FDA) granted accelerated approval of palbociclib in combination with letrozole in February 2015 and became the first CDK4/6 inhibitor to be approved as a cancer therapy by the FDA.²⁵ The label was later expanded to include aromatase inhibitor in this indication based on the follow-up of PALOMA-2 trial which was a Phase III study for post-menopausal patients with metastatic HR+/HER- BC receiving letrozole in combination with palbociclib versus patients receiving letrozole and placebo. The study showed that participants treated with Ibrance® in combination with letrozole had a greater PFS compared with patients treated with letrozole plus placebo (24.8 months vs. 14.5 months; $p<0.001$, respectively).²⁶ A regular approval was granted to palbociclib in February 2016 for a second indication: treatment of HR+, HER2-MBC in combination with fulvestrant in women with disease progression following endocrine therapy. This was following the success of Phase III PALOMA-3 trial, that showed that Ibrance® in combination with fulvestrant prolonged PFS (median PFS of 9.5 months) compared with placebo with fulvestrant (median PFS of 4.6 months; $p<0.0001$) in women with metastatic HR+/HER2- BC that had relapsed or progressed during endocrine therapy.²⁶

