3.2. Subgroups

Exploratory stratifications will be conducted (where adequate numbers of patients permit) to explore differences by eg, country, line of therapy (first or second), menopausal status, age (<55, 55-64, ≥65 years), combination therapy (ie, palbociclib plus letrozole/aromatase inhibitor vs. palbociclib plus fulvestrant), menopausal status, metastatic status (de-novo vs. recurrent disease) and metastatic site (visceral vs. non-visceral). For each stratification variable, the full analysis set will be segmented into non-overlapping subgroups based on the stratification variable values. The stratifications may not be meaningful, if there are no patients in some of the groups or there are many variables with a lot of missing data.

The exploratory stratifications will be conducted for the following study objectives describing the Palbociclib treatment, if enough data are available:

1. *Primary objectives: To determine clinical outcomes, including (but not limited to):*
 - *Proportion of patients who are progression free at multiple intervals (6, 12, 18 and 24 months).*
 - *Proportion of patients alive 1 and 2 years post palbociclib combination initiation - depending on availability of follow-up data.*

2. Secondary objectives:

- Objective response rate (ORR) - depending on availability of follow-up data
- To describe dosing and dose changes, interruptions, delays and discontinuations associated with palbociclib use in clinical practice. To describe supportive therapies received by patients while receiving palbociclib combination treatment.
- To summarize adjuvant therapies received for the treatment of early or locally advanced breast cancer (Stages 0-IIIa).
- To describe treatments received in the advanced/metastatic setting, before and after palbociclib combination use.
- To assess quality of life of patients receiving palbociclib combination treatment.

3. Exploratory objectives:

- To evaluate time to response (TTR), time to progression (TTP)/Progression free survival (PFS) associated with palbociclib combination treatment.
- To describe the first immediate subsequent treatment used following end of treatment with palbociclib.

The specific stratifications, and their corresponding reporting labels will be the following:

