6. STATISTICAL METHODOLOGY AND STATISTICAL ANALYSES

This is a descriptive study, and as such, no statistical testing will be conducted. Summary statistics for patient demographics, clinical characteristics, treatment patterns and QoL will be performed. Summary statistics for continuous variables will include number of observations, mean, standard deviation, median, 1st and 3rd quartiles, minimum, and maximum. Summary statistics for categorical data will include number of observations, counts and percentages. Kaplan-Meier analyses will be performed on time-to-event outcomes, eg, TTP, response and death.

Analyses will be conducted using Statistical Analysis System (SAS, version 9.4 or higher) or R version 3.5 or higher.

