6.2. Analysis for the Secondary Objectives

The objective response rate (ORR) will be described as shown in [Table Shell 2](#) and stratified in [Table Shells 3-9](#). The objective response will be defined as a state when either complete or partial response or stable disease has been reported as the overall tumor response in the last follow-up visit. ORR will be calculated as the ratio of the number of patients who are responsive to Palbociclib treatment (ie, have partial or complete response or stable disease for Palbociclib treatment recorded) over the number of patients who initiated Palbociclib treatment.³⁴ Censoring will be considered as described in [Section 3.1](#).

The demographic characteristics of the study population at breast cancer diagnosis for those receiving Palbociclib as first or second line therapy for metastatic/locally advanced BC will be described as shown in [Table Shells 10 and 11](#). Clinical characteristics of the study population at the initiation of Palbociclib treatment (baseline) those receiving Palbociclib as first or second line therapy will be described as shown in [Table Shells 12 and 13](#).

The dosing and dose changes, interruptions, delays and discontinuations associated with Palbociclib use in clinical practice will be described as shown in [Table Shell 14](#). The stratified tables will be presented as in [Table Shells 15 – 21](#).

The ten most common supportive therapies received by patients while receiving palbociclib combination treatment will be listed as shown in [Table Shell 22](#). The stratified tables will be presented as in [Table Shells 23 - 29](#).

The most common adjuvant therapies including systemic therapies, radiotherapy and surgeries will be described for early or locally advanced BC (stages 0-IIIa) patients as shown in [Table Shell 30](#). The stratified tables will be presented as in [Table Shells 31– 37](#).

The most common adjuvant therapies received by the advanced/metastatic BC patients (stages IIIB-IV) will be described both before and immediately after the first Palbociclib treatment as shown in [Table Shells 38 and 62](#), respectively. The stratified tables will be presented as in [Table Shells 39-45 and 63-69](#).

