Endocrine sensitivity	Palbociclib treatment characteristics (secondary endpoint)	At Palbociclib treatment initiation	CRF sheet: Palbociclib Treatment Initiation	
Endocrine sensitivity will be reported in five categories:
 
 Endocrine therapy naïve Endocrine sensitive Primary endocrine resistant Secondary endocrine resistant Not applicable
Combination therapy	Stratification variable	At Palbociclib treatment initiation	CRF sheet: Palbociclib Treatment Initiation	
 Palbociclib plus letrozole/aromatase (Palbociclib and either Anastrozole, Letrozole or Exemastane) Palbociclib plus fulvestrant
Line of endocrine therapy	Stratification variable	At Palbociclib treatment initiation	CRF sheet: Palbociclib Treatment Initiation	
Palbociclib as first or second line endocrine therapy
 
 first line second line
Prior chemotherapy for advanced/metastatic disease	Palbociclib treatment characteristics (secondary endpoint)	At Palbociclib treatment initiation	CRF sheet: Palbociclib Treatment Initiation	
 Yes No
Schedule 3 weeks on, 1 week off	Palbociclib treatment	At Palbociclib treatment initiation	CRF sheet: Palbociclib	Palbociclib treatment schedule

PFIZER CONFIDENTIAL

CT24-WI-GL03-RF02 2.0 Non-Interventional Statistical Analysis Plan For Primary Data Collection Study 01-Jun-2020

Page 39 of 172

09017760990673e30A5481150 Palbociclib Read On: 28-Mar-2023 09:56 (GMT)

Variable	Role	Time point(s)	Data source(s)	Operational definition
	characteristics (secondary endpoint)		Treatment Initiation	
 • Yes • No
Reasons for different schedule	Palbociclib treatment characteristics (secondary endpoint)	At Palbociclib treatment initiation At follow-up visits	CRF sheet: Palbociclib Treatment Initiation, Palbociclib Treatment Cycle Form	Reason for treatment schedule different from 3 weeks on, 1 week off 
 • To avoid toxicity • Due to line of therapy received • ECOG performance score • Age • Presence of comorbidities • Patient request • Metastases status • Stage at advanced breast cancer diagnosis • Concomitant medications • Other
Cycle interrupted	Palbociclib treatment characteristics (secondary endpoint)	At follow-up visits	Palbociclib Treatment Cycle Form	
 • Yes • No

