CT24-WI-GL03-RF02 2.0 Non-Interventional Statistical Analysis Plan For Primary Data Collection Study 01-Jun-2020

Page 41 of 172

09017760990673e30A5481150 Palbociclib Read On: 28-Mar-2023 09:56 (GMT)

Variable	Role	Time point(s)	Data source(s)	Operational definition
				
 • Presence of comorbidities • Patient request • Disease progression • Poor adherence • Developed resistance to endocrine treatment • Metastases status • Stage at the breast cancer diagnosis • Concomitant medications • Other
Accompanying endocrine treatments	Palbociclib treatment characteristics (secondary endpoint)	At Palbociclib treatment initiation	CRF sheet: Palbociclib Treatment Initiation	
Accompanying endocrine treatments during Palbociclib treatment:
 
 • Tamoxifen/NOLVADEX • Toremifene / FARESTON • Raloxifene / EVISTA • Anastrozole / ARIMIDEX • Letrozole / FEMARA • Exemestane / AROMASIN • Fulvestrant / FASLODEX • Goserlin Acetate / Zoal dex • Leuporelin / Lupron • Triptorelin / Decapeptyl • Degarelix / Firmagon
Interruption in the cycle	Palbociclib treatment characteristics (secondary endpoint)	At Palbociclib treatment discontinuation	CRF sheet: Palbociclib treatment discontinuation form	
Palbociclib treatment was interrupted:
 
 • Yes • no
Reasons for discontinuation	Palbociclib treatment characteristics (secondary endpoint)	At Palbociclib treatment discontinuation	CRF sheet: Palbociclib treatment discontinuation form	
Reasons for Palbociclib treatment discontinuation are categorised as:
 
 • Toxicities of side effects • Patient decision • Patient physical status • Disease progression • Completion of planned course of treatment • Developed resistance to endocrine treatment • Poor adherence • Death • Treatment related toxicity

PFIZER CONFIDENTIAL

CT24-WI-GL03-RF02 2.0 Non-Interventional Statistical Analysis Plan For Primary Data Collection Study 01-Jun-2020

Page 42 of 172

09017760990673e30A5481150 Palbociclib Read On: 28-Mar-2023 09:56 (GMT)

Variable	Role	Time point(s)	Data source(s)	Operational definition
				
 Non-treatment related toxicity Patient request Lost to follow-up Other

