Table Shell 14 - Descriptive summary table of Palbociclib treatment characteristics.

Missing	XX (xx%)
None, reason specified	XX (xx%)
Yes, specified treatment	XX (xx%)
Tamoxifen/NOLVADEX	XX (xx%)
Toremifene / FARESTON	XX (xx%)
Raloxifene / EVISTA	XX (xx%)
Anastrozole / ARIMIDEX	XX (xx%)
Letrozole / FEMARA	XX (xx%)
Exemestane / AROMASIN	XX (xx%)
Fulvestrant / FASLODEX	XX (xx%)
Goserlin Acetate / Zoalox	XX (xx%)
Leuprorelin / Lupron	XX (xx%)
Triptorelin / Decapeptyl	XX (xx%)
Degarelix / Firmagon	XX (xx%)
Interruption in the cycle	
Yes	XX (xx%)
No	XX (xx%)
Missing	XX (xx%)
Reasons for the cycle interruption	
Lab abnormalities	XX (xx%)
Decline in ECOG performance score	XX (xx%)
Presence of comorbidities	XX (xx%)
Patient request	XX (xx%)
Concomitant medications	XX (xx%)
Other	XX (xx%)
Missing	XX (xx%)
Modification in the dose and/or the schedule	
Dose modified	XX (xx%)
Schedule modified	XX (xx%)
Both modified	XX (xx%)
Neither modified	XX (xx%)
Missing	XX (xx%)
Reasons for the dose and/or schedule modifications	
To avoid toxicity	
Due to line of therapy received	XX (xx%)
ECOG performance score	XX (xx%)
Age	XX (xx%)
Presence of comorbidities	XX (xx%)
Patient request	XX (xx%)
Disease progression	XX (xx%)
Poor adherence	XX (xx%)
Developed resistance to endocrine treatment	XX (xx%)
Metastases status	XX (xx%)

PFIZER CONFIDENTIAL

Table Shell 14 - Descriptive summary table of Palbociclib treatment characteristics.

Stage at the breast cancer diagnosis	XX (xx%)
Concomitant medications	XX (xx%)
Other	XX (xx%)
Missing	XX (xx%)
Delays in the cycle	
Yes	XX (xx%)
No	XX (xx%)
Missing	XX (xx%)
Reasons for the delays in the cycle	
Lab abnormalities	XX (xx%)
Adverse events	XX (xx%)
Decline in ECOG performance score	XX (xx%)
Presence of comorbidities	XX (xx%)
Patient request	XX (xx%)
Concomitant medications	XX (xx%)
Other	XX (xx%)
Missing	XX (xx%)
Reasons for discontinuation	
Toxicities of side effects	XX (xx%)
Patient decision	XX (xx%)
Patient physical status	XX (xx%)
Disease progression	XX (xx%)
Completion of planner course of treatment	XX (xx%)
Developed resistance to endocrine treatment	XX (xx%)
Poor adherence	XX (xx%)
Death	XX (xx%)
Treatment related toxicity	XX (xx%)
Non-treatment related toxicity	XX (xx%)
Patient request	XX (xx%)
Lost to follow-up	XX (xx%)
Other	XX (xx%)
Treatment completed	
Yes	XX (xx%)
No, reason specified	XX (xx%)
Missing	XX (xx%)
Duration of Palbociclib treatment [days]	
N	XX (xx%)
Mean (SD)	xx.x (xx.x)
Q1, median, Q3	xx.x, xx.x, xx.x

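### Interruption, delay and dose-change percentages in SAP Table Shells 14-21 have no exposure base, so strata with different time on palbociclib are not comparable, and the interruption row may be taken from the wrong form

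*SAP*

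**What the plan says.** SAP 6.2 sends this secondary objective to Table Shell 14 overall and Shells 15-21 by stratum (numbers as in Annex 2): "The dosing and dose changes, interruptions, delays and discontinuations associated with Palbociclib use in clinical practice will be described as shown in" those shells. SAP 3.2 includes it among the objectives to be stratified, "To describe dosing and dose changes, interruptions, delays and discontinuations associated with palbociclib use in clinical practice", with the stated purpose of exploring differences by line, combination, country and other factors. No testing is planned. For categorical items SAP 6 provides that "Summary statistics for categorical data will include number of observations, counts and percentages".

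Each shell starts from a number of patients. It then has a Yes/No/Missing block for interruption, another under "Delays in the cycle", and a block "Modification in the dose and/or the schedule" with categories dose, schedule, both, neither and missing. Treatment duration in days appears further down. No row gives cycles, events per cycle, a fixed window or time to first event.

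Annex 1 Table 3 holds two interruption variables. "Cycle interrupted" is recorded at follow-up visits on the Treatment Cycle Form. The other, which has exactly the name of the shell row (*Interruption in the cycle*), is recorded once, at discontinuation, on the discontinuation form: "Palbociclib treatment was interrupted", yes or no. Treatment duration also comes from the discontinuation form.

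**The concern.** Interruption, delay and modification can each happen in any cycle, so a patient with more cycles has more chances to show at least one. A percentage of patients ever affected therefore mixes the rate of events with the length of treatment. Shells 15 and 16 set combinations and lines of therapy side by side, and a reader would naturally take the higher column as harder to keep on schedule. It may simply be the column treated longer.

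The second problem concerns the data source. If the interruption row is programmed from the variable whose name it bears, a patient still on palbociclib at 24 months may have no value. Those are the patients who stayed on treatment longest, and the share affected would differ between strata.

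**Working it through.** The plan states no time on palbociclib, no event rate and no precision target for these rows, so there is no figure of its own to reproduce. The check asks how far apart two groups appear when their per-cycle rate is identical.

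**Inputs from the documents**
- Median PFS (Protocol 6.1): 24.8 months (phase III) and 20.2 months (phase 2) with letrozole; 9.5 months with fulvestrant.
- Real-world 12-month progression-free rates (Protocol 6.1): 84.1% with an aromatase inhibitor, 79.8% with fulvestrant.
- Follow-up cap of 24 months (SAP 3.1).
- Cycle of 28 days, from the schedule of 3 weeks on and 1 week off in Annex 1.

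**Assumptions**
- PFS stands in for time on palbociclib, which is exponential.
- The per-cycle probability p is constant and the same in both groups. It is varied from 2% to 20%, because the documents give no rate.

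**Formulas**
- Hazard: L = ln 2 / median, or −ln(S12)/12.
- Mean exposure to 24 months: (1 − exp(−24L))/L.
- Ever affected: sum over k of P(K = k) × [1 − (1 − p)^k], where K is the number of cycles started, at most 26.

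**Mean exposure (months)**
- 24.8 vs 9.5: 17.5 vs 11.3, ratio 1.54.
- 20.2 vs 9.5: 16.4 vs 11.3, ratio 1.44.
- 84.1% vs 79.8%: 20.3 vs 19.3, ratio 1.05.

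**Percentage ever affected, letrozole/aromatase inhibitor vs fulvestrant**

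| p per cycle | 24.8 vs 9.5 months | 20.2 vs 9.5 months | 84.1% vs 79.8% at 12 months |
|---|---|---|---|
| 2% | 31.1 vs 21.4 | 29.3 vs 21.4 | 35.3 vs 33.8 |
| 5% | 58.4 vs 42.7 | 55.6 vs 42.7 | 65.0 vs 62.7 |
| 10% | 78.7 vs 62.4 | 75.9 vs 62.4 | 85.3 vs 83.1 |
| 20% | 90.6 vs 79.3 | 88.8 vs 79.3 | 94.8 vs 93.4 |
| Range of gap (points) | 9.6 to 16.3 | 7.9 to 13.5 | 1.4 to 2.3 |

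**Do the alternatives remove the gap?**
- Kaplan-Meier time to first event, censored at the end of palbociclib, estimates 1 − (1 − p)^6 after six cycles in either group. That is 11.4%, 26.5%, 46.9% and 73.8% for the four values of p.
- Events per cycle equals p in both groups while p is constant, but not if events cluster early. Take 15% in cycles 1-3 and 2% afterwards, with 24.8 vs 9.5 months. The first group starts 19.21 cycles on average, 2.92 of them in cycles 1-3: (0.15 × 2.92 + 0.02 × 16.28)/19.21 = 4.0 per 100 cycles. The second starts 12.71, with 2.81 in cycles 1-3: (0.15 × 2.81 + 0.02 × 9.90)/12.71 = 4.9 per 100 cycles. The artefact then runs the other way.

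**How many patients might lack a discontinuation form?** On the same proxy, the share still on palbociclib at 24 months is 0.5^(24/24.8) = 51% vs 0.5^(24/9.5) = 17%. From the real-world rates it is 0.841² = 71% vs 0.798² = 64%.

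**The case against.** Several counter-arguments have force.

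- **Exposure is shown.** Duration of treatment stands in the same shells, by stratum, so a reader can see that it is unequal. This is true, but it does not adjust the percentages, and duration comes from the same discontinuation form.
- **The aim is descriptive.** There is no test, the strata are exploratory, and the share of patients ever interrupted is a legitimate description of practice. This stands for the overall table. It does not cover columns set side by side to explore differences.
- **Ever/never is not written down.** The SAP gives no rule for turning several cycle records into one patient row. Ever/never is the natural reading, and without a rule the rows are undefined.
- **The form argument rests on a name.** The next row, reasons for interruption, matches a Treatment Cycle Form variable, and the delay row can only be the cycle-form variable. Another discontinuation-form variable, treatment completed, provides for censored patients, so some value may be expected for them. The case report form is not in the documents. This is why the point says that such patients may be missing, not that they will be.

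A reader might also infer that time on palbociclib differs two-fold. The trial medians do differ 2.1-fold (20.2/9.5) to 2.6-fold (24.8/9.5). They are PFS medians from separate trials, however, and under the 24-month cap mean exposure differs only 1.05- to 1.54-fold. A reader might equally carry these figures over to first versus second line. Nothing in the documents gives exposure by line, and the eligibility criteria do not tie a combination to a line beyond requiring licensed use.

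**Conclusion.** The point holds as a weakness of presentation in a secondary, descriptive objective, and it should be corrected. At an equal, constant per-cycle rate, the stratum with longer exposure shows the higher percentage in every scenario tried. The gap by combination may be as small as 1.4 points or as large as 16.3, depending on which of the documents' own PFS figures stands in for time on treatment. It shrinks if events concentrate in the first cycles. The documents do not support the claim that a large false difference will appear, or any size for the comparison by line.

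The source-form problem depends on none of these assumptions. As labelled, the interruption row points to the discontinuation form although cycle-level data exist. How many patients would be affected depends on whether a form is completed for those still on treatment at 24 months, which the documents do not say.

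**What to change.** Amend SAP 6.2, Annex 1 Table 3 and Shells 14-21 as follows.

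1. Derive interruption for all patients from the cycle-level variable on the Treatment Cycle Form. State that a patient counts as Yes if any recorded cycle is Yes. Compute duration up to the 24-month cut-off for patients still on treatment.
2. For comparisons between strata, add the Kaplan-Meier proportion with a first interruption, first delay and first dose or schedule modification by 6 and 12 months, censored at the end of palbociclib.
3. Show the number of cycles recorded and events per cycle as supporting rows, with a note that events per cycle is comparable only if the rate is roughly constant over cycles.
4. Keep the ever/never row as description.

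The cost is some extra programming and longer tables. No new data are needed, but cycle counts will be limited to cycles recorded at routine visits, and Annex 1 needs a definition of the cycle count because it has none now.

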6.3. Analysis for the Exploratory Objectives

For the exploratory analyses, time to response (TTR), time to progression (TTP)/ progression free survival (PFS) will be studied and results will be presented as shown in [Table Shell 54](#). The stratified tables will be presented as in Table Shells [55-61](#).

TTR is defined as the length of time (in days) from the initiation of Palbociclib treatment until the first reported disease response (complete or partial).³⁴ Censoring rules presented in [Section 3.1](#) will be applied.

TTP is defined as the length of time (in days) from the initiation of Palbociclib treatment until the first reported disease progression.³⁴ Patients will be censored at the end of Palbociclib treatment, death, time of withdrawal, or end of the 24-month follow-up, whichever occurs first, at the respective time point. Specifically, death is not included in TTP but is considered as censoring event.

PFS is defined as the length of time (in days) from the initiation of Palbociclib treatment until the first reported disease progression or death due to any cause, whichever occurs first.³⁴ The disease progression will be considered at the first follow-up visit after the Palbociclib treatment initiation when the overall tumor response recorded is progressive disease. Patients with no disease progression documented will be censored at the last available medical record entry or end of the follow-up period. Patients who are lost to follow-up will be censored at their last visit.

Survival analyses will be used to estimate time to event endpoints TTR, TTP and PFS. The results of the survival analysis will be presented as the Kaplan-Meier survival curves and their 95% confidence intervals (CIs) that will be calculated using the log-log transformation of the survival probabilities.³⁶ Together with the Kaplan-Meier plots, the number of patients at risk at time intervals (eg, 90 days or as seen appropriate for the study) will be reported. [Figure Shells 1 and 2](#) show how time to response (TTR) and progression free survival (PFS) will be visualized as Kaplan-Meier plots including the number of patients at different time intervals. Kaplan-Meier plots can be presented by other categories (see [Section 3.2](#)), if enough data are available. Moreover, the results of the survival analysis will be reported as a descriptive summary table including the number of patients at risk, the number of patients

with event and the number of censored patients, and the outcome's median, 1st and 3rd quartile with their 95% CIs, as shown in [Table Shell 54](#).

The first immediate subsequent treatments used following end of treatment with Palbociclib will be summarised as shown in [Table Shell 62](#). The stratified tables will be presented as in Table Shells [63-69](#).

